12.2.9.3. Hypoglycemic Events

The incidence, rate per 30 days and rate per year of hypoglycemic episodes (total, severe, and nocturnal as defined in Section 9.10) will be summarized by treatment at baseline, titration, maintenance, and overall study periods and at endpoint. The rate per 30 days between 2 visits is defined as the total number of episodes between the visits divided by the actual number of days between the visits, and then multiplied by 30 days.

The proportion of patients (with at least 1 hypoglycemic event (total, severe, nocturnal, and others) or incidence during the study will be summarized (counts and percentages) and analyzed using Fisher's exact test or the Pearson's chi-square test for the FAS population.

The rate of hypoglycemic episodes per 30 days and per year (total, severe, nocturnal, and others) will be analyzed at baseline, titration, maintenance, and overall study periods and at endpoint using the Wilcoxon test. In addition, the hypoglycemia rates will also be analyzed using a negative binomial model for the FAS population with terms for treatment, baseline HbA1c, prestudy treatment, and prestudy metformin or acarbose usage. The offset variables are log of patient's treatment duration/30 and log of patient's treatment duration/365.25 for the models analyzing hypoglycemia rate per 30 days and per year, respectively.

In addition, the total number of patients with at least 1 hypoglycemic episode divided by the total extent of exposure in patient-years will be calculated for the overall study period and summarized descriptively for each treatment group for total, severe, nocturnal, documented symptomatic, and asymptomatic hypoglycemia definitions only. Listings of hypoglycemic episodes will be presented by visit for each subject.

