5.2.8. Secondary Efficacy Outcomes and Methodology

The continuous secondary efficacy outcomes include:

- actual and change in HbA1c from baseline to 6, 12, and 18 weeks or LOCF
- 7-point SMBG measurements and change from baseline to each visit (expressed as plasma-equivalent glucose values), as listed in the Study Schedule (see ABES Study Protocol Attachment 1)
 - premeal for each meal
 - postmeal for breakfast and lunch
 - bedtime
 - 3 am
- summaries of 7-point SMBG (actual and change from baseline)
 - daily mean BG level (average across all 7 time points)
 - daily mean premeal BG level (before breakfast, lunch, dinner)
 - daily mean postprandial BG level (breakfast, lunch and bedtime)
 - bedtime to 3 AM excursion
- inpatient variability as measured by the SD of the 7-point SMBG.

- actual and change from baseline total insulin, basal insulin, and mealtime insulin lispro doses in U/day and U/kg/day
- actual and change from baseline in weight and BMI
- patient-reported outcomes as reflected in responses to ITSQ.

The analysis of the continuous secondary efficacy variables will be performed using the same MMRM model with treatment (LY2963016, Lantus®), pre-study treatment (Lantus®-bolus, other basal-bolus, premixed insulin), and pre-study metformin or acarbose usage (metformin only, acarbose only, or neither), visit, and interaction between visit and treatment as fixed effects; the baseline value of the response variable and the baseline HbA1c level as covariates; and a random effect for patient, with the FAS population.

The proportions of subjects achieving HbA1c target values (HbA1c <7.0% and ≤6.5%) at any point during the study (Weeks 6, 12, 18, 24, and 24-week endpoint [LOCF]) will be analyzed using Fisher's Exact test or Pearson's Chi-square test.

A listing of 7-point SMBG and 4-point SMBG will be presented for all the randomized subjects.

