Pseudo-hypoglycemia: an event during which the person with diabetes reports any of the typical symptoms of hypoglycemia with a measured plasma glucose concentration >70 mg/dL (> 3.9 mmol/L) but approaching that level.

Besides the hypoglycemic categories listed above, total hypoglycemic event will be defined as follows:

Total hypoglycemic event: any event which is either documented symptomatic hypoglycemia, asymptomatic hypoglycemia, probable symptomatic hypoglycemia or severe hypoglycemia.

For each category of hypoglycemia event, the incidence, the number of hypoglycemic events per patient, the rate of hypoglycemic events per year (that is, the number of hypoglycemic episodes per patient per patient year [365.25 days]) will be calculated. These measures will be summarized at baseline, titration, maintenance, and overall study periods and at endpoint.

The proportion of patients with at least 1 hypoglycemic event (total, severe, nocturnal, and others) or incidence during the study will be summarized (counts and percentages) and analyzed using Fisher's exact test or the Pearson's chi-square test for the FAS population.

Logistic regression will be used as a sensitivity analysis of the incidence of hypoglycemia. The model will have presence or absence of hypoglycemia as the dependent or response variable and treatment, baseline HbA_{1c}, pre-study treatment (Lantus®-bolus, other basal-bolus, premixed insulin), and pre-study metformin or acarbose usage (metformin only, acarbose only, or neither) as the independent terms in the model.

The rate of hypoglycemic episodes per year (total, severe, nocturnal, and others) will be analyzed at baseline, titration, maintenance, and overall study periods and at endpoint using the Wilcoxon test. In addition, the hypoglycemia rates will also be analyzed using a negative binomial model for the FAS population with terms for treatment, baseline HbA_{1c}, pre-study treatment (Lantus®-bolus, other basal-bolus, premixed insulin), and pre-study metformin or acarbose usage (metformin only, acarbose only, or neither).

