For each subgroup listed above, the change in weight from baseline to 24-week will be analyzed using the same methodology as the subgroup analysis of HbA_{1c}.

Additional subgroup analyses will be carried out on selected safety outcomes:

- a) total, severe or nocturnal hypoglycemia at 24-week endpoint and for the overall 24-week period (rates and incidence)
- b) treatment-emergent antibody response (TEAR) at 24-week endpoint and for the overall 24-week period
- c) detectable insulin antibodies at 24-week endpoint and for the overall 24-week period
- d) categories of adverse events:
 - treatment-emergent adverse events (TEAEs) (overall incidence and preferred terms with $> 5\%$ incidence)
 - TEAEs related to study drug (overall incidence)
 - special topic assessment of allergic events (overall incidence)
 - injection site reactions (overall incidence)
 - serious adverse events (overall incidence)

For rates and incidence of hypoglycemia (total, nocturnal, severe) and categories of adverse events, the same set of 11 subgroups used to analyze change in HbA_{1c} and change in weight will be analyzed.

For each categorical safety outcome and subgroup listed above, the proportion of patients with an event will be compared between treatments for the FAS. Within each subgroup, treatments will be compared using the Mantel-Haenszel test and the odds ratio and p-value from this test will be reported. The homogeneity of the odds ratios across subgroups will be assessed using the Breslow-Day test.

For the 11 subgroups listed above, the rate of total, severe or nocturnal hypoglycemia per year at the 24-week endpoint and for the overall 24-week period will be analyzed. Within each subgroup, treatments will be compared using the negative binomial (NB) model with treatment as the only factor. The NB mean for each treatment and their ratio with corresponding 95% confidence interval will be presented. Additionally, within each subgroup the rates will be compared using the Wilcoxon test. The significance of the subgroup-by-treatment interaction will be evaluated using a negative binomial model with factors treatment, subgroup and treatment-by-subgroup interaction. The negative binomial model will be implemented using the SAS PROC GENMOD with natural logarithm of exposure time (in days) as an offset variable. The above subgroup analysis will be performed and p-values will be provided if there are at least a total of 20 events in the combined treatment groups.

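### The subgroup negative binomial models for hypoglycemia rate omit the covariates of the main model; aligning them costs little and gains precision if those covariates are prognostic

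*SAP*

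**What the plan says.** For hypoglycemia rates, SAP 5.2.12 states: "Within each subgroup, treatments will be compared using the negative binomial (NB) model with treatment as the only factor". The interaction "will be evaluated using a negative binomial model with factors treatment, subgroup and treatment-by-subgroup interaction". Both use log exposure in days as offset. The analysis is run only if at least 20 events occur in the two arms combined.

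The main analysis of the same outcome is richer. In SAP 5.2.11.2, "the hypoglycemia rates will also be analyzed using a negative binomial model for the FAS population with terms for treatment, baseline" HbA1c and the two pre-study factors. Protocol 12.2.9.3 specifies the model "with terms for treatment, baseline HbA1c, prestudy treatment, and prestudy metformin or acarbose usage".

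The HbA1c subgroup model, also in SAP 5.2.12, keeps all three covariates. It adds the rule that a stratification variable serving as the subgroup is entered only once. Under Protocol 9.3, pre-study treatment and metformin or acarbose use are randomisation factors. The third randomisation factor, screening HbA1c stratum, is represented in the main model only through continuous baseline HbA1c.

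**The concern.** Hypoglycemia is part of a named secondary safety objective (Protocol 6.2, SAP 4.2). The subgroup rate ratios will be read beside the overall ratio, yet the two come from differently specified models. A gap between them can therefore reflect chance covariate imbalance within a subgroup as well as a real difference in effect.

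If baseline HbA1c and prior regimen predict hypoglycemia, the treatment-only fits leave that variation in the dispersion. The confidence intervals are then wider, and the interaction test weaker, than the collected data allow. The sponsor already treats these covariates as worth including in the main model.

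**Working it through.** **The plan's own figure.** No power or precision figure is given for these analyses. The trial size that sets their scale does reproduce: 2 × (1.960 + 0.842)² × 1.05² / 0.40² = 108.2, so 109 completers per arm; 109 / 0.85 = 128.2, so 129 randomised per arm, 258 in total.

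**What is dropped.** The three covariates amount to five parameters: one slope for HbA1c and two contrasts for each three-level factor. The within-subgroup fits drop all five. For 4 of the 11 subgroup factors (both entry-HbA1c splits, pre-study treatment, metformin or acarbose use), the subgroup term in the interaction model puts that factor back, in categorical form for HbA1c. The offset is not an issue: log days and log(days/365.25) differ by a constant, which moves only the intercept.

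**Analytic check.** The variance of a log rate ratio is proportional to 1/μ + k, where μ is events per patient and k the dispersion. If covariates remove a share R of k, the SE ratio (adjusted/unadjusted) is √[(1/μ + (1−R)k) / (1/μ + k)]. All inputs are assumed. With k = 1 and R = 0.2:

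- μ = 20: √(0.85/1.05) = 0.90
- μ = 2: √(1.30/1.50) = 0.93
- μ = 0.05: √(20.8/21.0) = 0.995

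So a gain needs both frequent events and prognostic covariates.

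**Simulation of one adjusted model on the whole FAS against the planned treatment-only fits.** Assumptions: 258 patients, 15% dropout, residual dispersion 0.8, 600 trials per scenario. Modest effects: log-rate slope −0.15 per HbA1c point, regimen rate ratio up to 1.35. Strong effects: −0.30 and up to 2.0. Ratio of the empirical SD of the log rate ratio, adjusted/planned, at mean 4 / mean 15 events per 24 weeks:

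| | No effect | Modest | Strong |
|---|---|---|---|
| Subgroup, 20 per arm | 1.02 / 1.01 | 0.98 / 0.99 | 0.90 / 0.81 |
| Subgroup, 64 per arm | 1.02 / 1.00 | 0.97 / 0.96 | 0.87 / 0.86 |
| Interaction (range) | 1.01-1.02 | 0.96-0.99 | 0.82-0.91 |

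A separate run of 250 trials per scenario gave 0.99-1.02, 0.92-1.01 and 0.82-0.91. These ratios carry a Monte Carlo error of a few percent. A third run, of 400 trials, gave 1.04 for the interaction with no covariate effect. Repeating that case with many more trials gives 1.02, so I take the loss as about 2%.

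**Adjusting inside each subgroup instead.** In the 400-trial run (40 events per year), adding the covariates within a subgroup of 20 per arm gave SD ratios of 1.09 (no effect), 1.06 (modest) and 0.92 (strong; slope and regimen effects set separately for that run). Spending five parameters inside a small cell can lose precision; the whole-FAS model largely avoids this.

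**Severe hypoglycemia.** Protocol section 5 reports 4.9% and 4.5% of patients over 52 weeks in the earlier type 1 study, about 4.7% on average. Pro rata, 258 × 0.047 × 24/52 = 5.6, or about 6 patients. Unless repeat events are common, the 20-event minimum would not be met.

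**The case against.** The simpler model is defensible. SAP 5.2.12 treats its safety subgroups uniformly without covariates. The overall hypoglycemia analysis also leads with unadjusted tests, and the adjusted model is an addition. Protocol 12.2.10 specifies a subgroup model only for HbA1c, so the hypoglycemia subgroups are SAP additions. They have no multiplicity control and trigger no decision rule. The size of any gain rests on inputs that the documents do not supply. All of this stands, and it limits the point to a minor one. The loss from adjusting within small cells is real, but it largely falls away with a whole-FAS model.

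A reader might infer more than the documents support:

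- **That the subgroup ratios are biased.** With a log link and randomised treatment, adjusted and unadjusted ratios target the same quantity when the treatment ratio does not vary with the covariates. This covers subgroups defined at baseline. Time of basal injection may not be one, and adjustment would not settle that.
- **That every confidence interval is widened.** With rare events or non-prognostic covariates there is no gain, or a slight loss.
- **That the negative binomial interaction test is the only consistency check.** For incidence, 5.2.12 also plans Mantel-Haenszel comparisons and the Breslow-Day test; rates are also compared within subgroups by Wilcoxon test.
- **That the weight subgroup model omits baseline weight.** SAP 5.2.12 says weight "will be analyzed using the same methodology as the subgroup analysis of" HbA1c, which read literally names only baseline HbA1c. But SAP 5.2.1 sets a general rule, naming weight, that the response's own baseline is a covariate, and 5.2.8 includes "the baseline value of the response variable and the baseline" HbA1c. Nothing in 5.2.12 overrides this.

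**Conclusion.** The inconsistency is real and unexplained, in both the within-subgroup and the interaction models. Its consequence is conditional. For total and nocturnal hypoglycemia, a whole-FAS adjusted model would lower the SD of the subgroup or interaction log rate ratio by about 0-8% with modest covariate effects and 9-18% with strong ones (one table cell, 0.81, lies just outside). The cost is about 2% if the covariates have no effect. For severe hypoglycemia, expect little or nothing.

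These figures rest on assumed event rates, dispersion and covariate effects, and the smallest differences lie within simulation error. The case for change is an asymmetric trade: a small possible loss against a possibly useful gain, with data already collected. It is a minor improvement to secondary safety analyses and does not affect the primary conclusion.

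**What to change.** In SAP 5.2.12, for each subgroup factor, fit one negative binomial model on the whole FAS with treatment, subgroup, their product, baseline HbA1c, pre-study treatment, pre-study metformin or acarbose use, and the log-exposure offset. A stratification factor that is itself the subgroup enters once, as in the HbA1c subgroup model. Take the within-subgroup rate ratios and 95% CIs as contrasts from this model, and the interaction test from the same fit. Keep the 20-event minimum. The treatment-only fits can stay as a sensitivity analysis. If the sponsor prefers the simpler model, one sentence of justification would do.

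The cost is SAP wording and a few lines of code. The downside is that one dispersion parameter and common covariate effects are assumed across subgroup levels; the planned interaction model already assumes a common dispersion.

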5.2. Statistical and Analytical Plans

5.2.1. General Considerations

All data will be entered, verified, and archived at a contract research organization (CRO) external to Lilly and/or at Lilly. Data listings, summaries, and analyses will be performed by a CRO and/or by Lilly under the guidance and approval of statisticians at Lilly. Statistical analysis of this study will be the responsibility of Lilly.

Any change to the data analysis methods described in the protocol will require an amendment ONLY if it changes a principal feature of the protocol. Any other change to the data analysis methods described in the protocol, and the justification for making the change, will be described in the statistical analysis plan and/or in the clinical study report (CSR). Additional exploratory analyses will be conducted, as deemed appropriate.

The patient populations used in the study are described below:

1. All Patients Entered: all patients who entered this study and completed Visit 1.
2. All Randomized: all patients who were randomized to a treatment arm.
3. Full Analysis Set (FAS): based on the intent to treat (ITT) principle, all patients who were randomized and who have taken at least one dose of study medication. Patients are assigned to the treatment arm to which they were randomized.
4. Per-protocol (PP): patients in the FAS/ITT population who also meet the following criteria:
 - a. violate no inclusion or exclusion criteria
 - b. have not discontinued from the study prior to 24 weeks
 - c. have not been off study medication for more than 10 consecutive days during the treatment period
 - d. have not received chronic (lasting longer than 14 consecutive days) systemic glucocorticoid therapy (excluding topical, intra-articular, intraocular, and inhaled preparations)

Unless otherwise specified, listings will be prepared using all randomized patients. Efficacy and safety analyses will be conducted using the FAS population. Selected analyses will be conducted using the All Randomized population and the PP population.

Unless otherwise noted, all tests of treatment effects will be conducted at a 2-sided alpha level of 0.05, and confidence intervals (CIs) will be calculated as 2-sided 95% CIs. All tests of interactions between treatment groups and other factors will be conducted at a 2-sided alpha level of 0.05. No adjustments for multiplicity will be performed. See Section 5.2.7 for the gate-keeping strategies used for primary/secondary endpoints.

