5.2.12. Subgroup Analyses

The consistency of the treatment effect for the change in HbA_{1c} level will be assessed in the following subgroups in the FAS population if there are sufficient numbers of patients in each treatment by subgroup (e.g. 20 patients per cell):

- Entry HbA_{1c} levels (<7%, ≥7%)
- Entry HbA_{1c} levels (<8.5%, ≥8.5%)
- Pre-study treatment (Lantus[®]-bolus, other basal-bolus, premixed insulin)
- Entry BMI (<30, ≥30)
- Entry BMI (<25, ≥25)
- Entry age (<65, ≥65)
- Entry age (<75, ≥75)
- Gender
- Prestudy metformin or acarbose use (metformin only, acarbose only or neither)
- Time of basal insulin injection (daytime, evening/bedtime)
- Renal function, as estimated by estimated glomerular filtration rate (EGFR) using the MDRD formula (see [Appendix 2](#)). The following EGFR categories will be used:

- normal or increased GFR: EGFR (≥ 90 mL/min/1.73 m²)
- mild reduction in GFR: EGFR (60 to 89 mL/min/1.73 m²)
- Moderate reduction in GFR: EGFR (30 to 59 mL/min/1.73 m²)
- Severe reduction in GFR: EGFR (15 to 29 mL/min/1.73 m²)
- Kidney failure: EGFR (< 15 mL/min/1.73 m²).

The categories severe reduction in GFR and kidney failure will be combined if there are fewer than 20 patients in either of these categories.

The change in HbA_{1c} from baseline to 24-week endpoint will be analyzed using MMRM with treatment, visit, prestudy treatment, prestudy metformin or acarbose usage, subgroup, subgroup-by-treatment interaction, subgroup-by-visit interaction, treatment-by-visit interaction, and treatment-by-visit-by-subgroup interaction as fixed-effects, the baseline value of HbA_{1c} as a covariate, and a random effect for patient for the FAS population. If the subgroup is one of the stratification variables, then the subgroup will only be included once in the model. A significant treatment-by-subgroup interaction ($p < .05$) may be indicative of a differential treatment effect across levels of the subgroup, necessitating further exploration of the nature of the interaction.

The contrast from the MMRM model with the OM option using PROC Mixed in SAS above will be used to obtain the LSmeans for change in HbA_{1c} levels from baseline to Week 24 within each treatment at each level of the subgroup. Additionally, the difference of these LSmeans between treatment groups with 95% confidence interval and p-values will be presented.

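### The hypoglycemia-rate subgroup comparisons in the SAP require 20 pooled events but no minimum number of patients, so in a sparse subgroup level the negative binomial interval would be too narrow

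*SAP*

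**What the plan says.** SAP 5.2.12 sets two different entry conditions for its subgroup analyses.

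- For change in HbA1c, consistency is assessed "if there are sufficient numbers of patients in each treatment by subgroup (e.g. 20 patients per cell"). Weight follows the same methodology.
- For total, severe and nocturnal hypoglycemia, the SAP takes "the same set of 11 subgroups used to analyze change in" HbA1c and weight. For the yearly rates it says "Within each subgroup, treatments will be compared using the negative binomial (NB) model with treatment as the only factor", and it presents the two means and their ratio with a 95% confidence interval. It adds that "within each subgroup the rates will be compared using the Wilcoxon test", and it tests the subgroup-by-treatment interaction in a further negative binomial model. The paragraph closes with its own condition: the analysis is done and "p-values will be provided if there are at least a total of 20 events in the combined treatment groups".

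The SAP does not say whether the 20 events are counted within a subgroup level or over the whole trial. The only other size rule merges the two lowest eGFR levels when either has fewer than 20 patients, and it sets no minimum for the merged level. SAP 5.2.1 fixes the nominal level: "all tests of treatment effects will be conducted at a 2-sided alpha level of 0.05" unless otherwise noted, and "No adjustments for multiplicity will be performed".

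**The concern.** The number of events is a poor measure of information when events recur in the same patient. SAP 5.2.11.2 counts any glucose of 70 mg/dL or below, with or without symptoms, and Protocol 7.2.3 expects fasting, premeal and bedtime checks every day. Twenty events can therefore come from very few people.

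A negative binomial comparison rests on an estimate of how much patients differ from one another, and only more patients improve that estimate. With few patients the estimate tends to be too low, while the usual interval treats it as known. A level judged too small for an HbA1c comparison could then still produce a hypoglycemia rate ratio with an interval that looks more precise than it is. Hypoglycemia is a named secondary safety comparison, so a false subgroup difference between two highly similar insulins would need explaining.

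**Working it through.** **Inputs from the documents.** Threshold of 20 pooled events; negative binomial model with treatment only and log exposure as offset; two-sided 5% (SAP 5.2.1 and 5.2.12); 1:1 allocation (Protocol 9.3); 258 patients, at most 400 (SAP 5.1). The plan states no operating characteristic for these tests beyond the nominal 5%, so there is no figure to reproduce.

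**Assumed, because the documents do not give them.** Mean events per patient over 24 weeks, dispersion k, and the size of each subgroup level.

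**Step 1: can a few patients reach 20 events?** Four daily checks over 24 weeks give 4 × 7 × 24 = 672 readings per patient. Four patients with five events each make 20. In simulation, at a mean of 5 events per patient the threshold is met in 77-87% of levels with 3 per arm and 98-100% with 5 per arm. At a mean of 20 or 40 it is met in 97-100% with only 2 per arm.

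**Step 2: severe events.** The Protocol introduction reports 4.5% and 4.9% of patients with severe hypoglycemia over 52 weeks in the earlier type 1 study. At a constant hazard, the expected number of patients with an event in 24 weeks is N × (1 − (1 − p)^(24/52)). This is 5.4 to 5.9 for N = 258 and 8.4 to 9.2 for N = 400, over the whole trial. Twenty severe events within one level should be rare.

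**Step 3: what the threshold controls.** With n patients per arm, equal exposure and E1 and E2 events in the arms,

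Var(log rate ratio) = 1/E1 + 1/E2 + 2k/n.

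The event threshold limits only the first two terms. For n = 3, a mean of 20 and k = 1, these are 1/60 + 1/60 = 0.033, against 2k/n = 0.667. About 95% of the variance (0.667/0.700) depends on the number of patients and on an estimate of k taken from six people.

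**Step 4: rejection rate under equal rates.** Gamma-Poisson counts were simulated with equal means, 1,000 to 3,000 data sets per setting. The model was fitted by maximum likelihood with a common dispersion. The Wald test corresponds to the usual 95% interval. Results are conditional on at least 20 pooled events in the level.

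| Patients per arm | Wald | Likelihood ratio |
|---|---|---|
| 2 | 17-31% | 14-24% |
| 3 | 14-23% | 11-16% |
| 5 | 9-14% | 8-10% |
| 10 | 7-10% | 6-8% |
| 20 | 5-9% | 5-7% |

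The settings are means of 5 to 40 and k of 0.5 to 1. The likelihood-ratio ranges and the Wald range at 5 per arm also take in settings with a mean as low as 2 or k up to 2.

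**Step 5: the companion tests.** The Wilcoxon test rejected in 0-4% of cases at 3 to 8 per arm (mean 10, k = 1). The interaction test, with a level of 2 to 5 per arm inside a trial of 258, rejected in about 7-9%. It is less affected because the large level supplies most of the information on k.

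**Step 6: how small might a level be?** Exclusion criterion 26 removes creatinine above 2.0 mg/dL. Putting 2.0 into the MDRD formula in SAP Appendix 2, without the race factor, gives 175 × 2.0^−1.154 = 78.64.

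- Man aged 90: 78.64 × 90^−0.203 = 31.5.
- Woman aged 30: 78.64 × 30^−0.203 × 0.742 = 29.3.
- Woman aged 80: 78.64 × 80^−0.203 × 0.742 = 24.0.

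Among patients who meet the criterion, the level below 15 should therefore be empty at entry, and the 15-29 level is confined to women near the creatinine limit. Age 75 or over, BMI 30 or over and acarbose only may also be thin. None of this gives a count.

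**The case against.** The strongest reply is that a patient-count condition already applies. The opening sentence of Protocol 12.2.10 asks for a sufficient number of patients in each treatment-by-subgroup cell and does not name an outcome, so the 20-event rule could be read as an addition to it. No text says that the event rule replaces the patient rule. This stands as far as it shows the wording to be ambiguous. It does not settle the matter: Protocol 12.2.10 goes on to specify only an HbA1c model, SAP 5.2.12 ties its patient condition to HbA1c, and the hypoglycemia-rate paragraph states a condition of its own.

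A second reply is that the large rejection rates belong to a corner. They need 2 to 5 patients per arm and the Wald test, and the SAP does not say which negative binomial test supplies the p-value. For the 24-week endpoint, if that means the last six weeks (an assumption), a mean of 5 becomes 5 × 6/24 = 1.25. The threshold is then met in only 0-1% of levels at 2-3 per arm and 7-10% at 5 per arm. All of this stands.

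A reader might infer that these tests will in fact run in tiny subgroups and that a spurious safety difference is a likely product. The documents do not support that: they give no subgroup sizes or event rates, and the Wilcoxon and interaction results would be reported beside the rate ratio.

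**Conclusion.** The rule as written lets the within-level negative binomial comparison go ahead on events alone, and for total hypoglycemia the threshold is a weak screen on the number of patients. The same may hold for nocturnal hypoglycemia. If a level has about 2 to 5 patients per arm, the nominal 5% Wald test rejects in roughly 9-31% of cases under equal rates, and the likelihood-ratio test in roughly 8-24%. By 10 per arm the Wald excess is a few percentage points, and at 20 per arm it is small.

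These figures rest on the assumed event rates and dispersion. Whether any level will be that sparse is possible but not shown. Severe hypoglycemia, the overall hypoglycemia comparison, the sample size and the noninferiority conclusion are not touched. No decision rule hangs on these subgroup results, so the severity is minor.

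**What to change.** In SAP 5.2.12, add to the hypoglycemia-rate paragraph that the negative binomial rate ratio, its interval and its p-value within a subgroup level are reported only if two conditions hold: at least 20 events counted within that level, and the patient-count condition already used for HbA1c (for example 20 patients) met in each treatment-by-level cell. Below that, show patients, events, exposure and crude rates by arm. This also settles where the 20 events are counted.

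The cost is one sentence. Some small levels would get descriptive hypoglycemia results only, including levels of 10 to 19 per arm where the excess is modest. The descriptive display would be new: SAP 5.2.12 does not promise one for HbA1c below its own condition.
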